##### 4.2.2 Key Secondary Endpoints

- Progression to severe disease or death, defined by the WHO OSCI score of 5 or above within 35 days of first dose.
- Progression to intubation or death, defined by the WHO OSCI score of 6 or above within 35 days of first dose.
- Death within 35 days of first dose.

**4.2.3 Secondary Endpoints**

- Recovery, where recovery is defined as the WHO OSCI score of 1 or below, with no rebound at subsequent assessments, at Days 7, 14, 21 and 28.
- Hospital discharge at Days 7, 14, 21 and 28.
- Improvement across the entire WHO OSCI at Days 7, 14, 21 and 28.
- Changes in Breathlessness, Cough and Sputum Scale (BCSS) score during the study period, including disaggregated breathlessness and cough scores.
- Changes in National Early Warning Score (NEWS)2 during the hospitalisation period.
- Daily assessment of COVID-19 symptoms and limitation of usual activities.
- Quality of life measured using EuroQol 5-dimension 5-level (EQ-5D-5L).
- Long-COVID-19 symptoms.
- Safety and tolerability – vital signs, adverse events (AEs) and concomitant medications.

**4.2.4 Exploratory Endpoint**

CCI

CCI

**5 Study Methods****5.1 General Study Design and Plan**

610 adults,  $\geq 18$  years of age with Severe Acute Respiratory Syndrome Coronavirus 2 (SARS-CoV-2) infection confirmed by a positive virus test using a validated molecular assay e.g. Reverse Transcription Polymerase Chain Reaction (RT-PCR) or antigen assay, e.g. Sofia 2 SARS Antigen FIA, who are hospitalised due to COVID-19 and require oxygen therapy, either via nasal prongs or a mask, but do not require high-flow nasal oxygen therapy, non-invasive ventilation (Continuous Positive Airway Pressure [CPAP] or /bilevel positive airway pressure [BiPAP]) treatment or endotracheal intubation will be randomised 1:1 to receive SNG001 two syringes (305 patients) or placebo two syringes (305 patients).

Patients will receive a dose of SNG001 or placebo once a day for 14 days and will be followed for up to 90 days after the first dose of study medication. Study data will be collected from patients daily until day 35, as per the study schedule.

**5.2 Randomisation and Blinding**

This is a double-blind study. Patients will be randomised to one of two treatment groups (SNG001 or placebo) in a 1:1 randomisation ratio. Randomisation is stratified by study site.

- Arm 1: 305 patients - SNG001 - contents of 2 syringes\* per dose.
- Arm 2: 305 patients - Placebo - contents of 2 syringes† per dose.

\* Each syringe contains CCI mL of SNG001 nebuliser solution containing CCI MIU/mL interferon- $\beta$ 1a.

† Each syringe contains CCI mL of formulation buffer.

## Statistical Analysis Plan (RotW)

Final v1.0, 08FEB2022

SG018

Data provided for Data Safety Monitoring Committee (DSMC) meetings will be unblinded, starting from the second DSMC meeting as per DSMC charter version 2. An independent statistical team will be responsible for generating the unblinded outputs provided to the DSMC and will not be involved in any future decisions regarding study conduct.

Unblinded data will also be provided for the futility analysis and will therefore be provided by an independent statistical team who will not be involved in any future decisions regarding study conduct. Futility analysis outputs will be reviewed by the DSMC acting as the Independent Data Monitoring Committee (IDMC), as documented in the DSMC charter.

The main study team will remain blinded until the primary analysis, which will be conducted once all patients have withdrawn, or completed the day 35 assessment.

For further information regarding study unblinding, refer to the study unblinding plan.

### 5.3 Derived variables

Unless otherwise specified, baseline is defined as the last non-missing pre-treatment assessment prior to first dose. For patients who are randomised but do not receive any study treatment baseline will be defined as the pre-treatment assessment.

#### 5.3.1 Derivations from the Ordinal Scale for Clinical Improvement

##### 5.3.1.1 Hospital Discharge

Hospital discharge will be defined as the first post baseline score of  $\leq 2$  which is sustained for a minimum of 7 days and up to the date of the Day 35 assessment or study withdrawal, whichever occurs first (see [Section 15](#) for changes from the protocol) according to the WHO 9-point Ordinal Scale for Clinical Improvement (OSCI)[1]. If any OSCI assessments are missing following discharge, sustained hospital discharge will be confirmed by the subject's location on the assessment day, which will be recorded in the CRF as "In Hospital" or "Not in Hospital" and may be entered retrospectively. If location is missing, the patient will be assumed to be not in hospital under the assumption that any hospitalisations prior to the last completed assessment will be recorded in the clinical database. This will not include assessments missing following study withdrawal if study withdrawal occurs within 7 days of hospital discharge. If a patient withdraws from the study within 7 days of hospital discharge, they will not be considered as discharged. Hospital discharge will be derived for all scheduled post-baseline assessments up to day 28.

Time to hospital discharge (in days) for discharged patient will be calculated as the following:

$$\text{Date of first hospital discharge} - \text{date of randomisation} + 1$$

Because OSCI score is collected up to day 35, the latest possible hospital discharge date will be at the Day 28 assessment (because it must be sustained for a minimum of 7 days). Patients who die will be administratively censored at the maximum time to hospital discharge. Patients who are not discharged for a minimum of 7 days will be considered censored at the date of their last OSCI assessment of 3 or above. Time to censoring will be calculated as the following:

Date of last OSCi assessment >2 on or before Day 28 – date of randomisation + 1.

### 5.3.1.2 *Recovery*

Recovery will be defined as the first post baseline OSCi score of  $\leq 1$  which is sustained for 7 days (see [Section 15](#) for changes from the protocol). A maximum of 3 missing OSCi assessments will be permitted during the rebound period, provided all observed OSCi assessments in the rebound period are 1 or below. If more than 3 assessments are missing the patient will not be considered as recovered at that date and sustained recovery will be reassessed at the subsequent OSCi assessment  $\leq 1$ , if applicable, or otherwise censored according the rules below. This will not include assessments missing due to study withdrawal. If a patient withdraws from the study during the 7 day rebound period they will be considered not recovered. Recovery will be derived for all scheduled post-baseline assessments up to Day 28.

Time to recovery (in days) for recovered patients will be calculated as the following:

Date of first OSCi score of  $\leq 1$  – date of randomisation + 1.

Because OSCi score is collected up to day 35 the latest date of recovery will be at the Day 28 assessment. Patients who die will be administratively censored at the maximum time to recovery. Patients who potentially recover, but cannot be confirmed due to missing data (i.e. after an OSCi  $\leq 1$  all observed assessments in the subsequent 7 days were  $\leq 1$  but more than 3 assessments were missing) will be censored at the assessment immediately prior to the potential date of recovery. All other patients who do not recover for a minimum of 7 days will be considered censored at the date of their last OSCi assessment of 2 or above on or before day 28. Time to censoring will be calculated as the following:

Date of last OSCi assessment >1 on or before day 28 – date of randomisation + 1

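### SAP 5.3.1.2 ignores the recorded hospital location on missed OSCI days, so a patient known to be back in hospital for up to 3 missed days can count as having sustained recovery

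*SAP*

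**What the plan says.** SAP 5.3.1.2 defines recovery as the first post-baseline OSCI score of 1 or below "which is sustained for 7 days". On gaps in that window it says "A maximum of 3 missing OSCi assessments will be permitted during the rebound period, provided all observed OSCi assessments in the rebound period" do not exceed 1. If more than 3 are missing, recovery is not accepted at that date and is tested again from the next score of 1 or below. A patient whose possible recovery is never confirmed because of missing scores "will be censored at the assessment immediately prior to the potential date of recovery". The section does not mention hospital location.

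SAP 5.3.1.1 handles the same kind of gap differently for the other primary endpoint. When scores are missing after discharge, "sustained hospital discharge will be confirmed by the subject's location on the assessment day". That location is a two-value CRF field (in hospital or not) that sites may complete afterwards. If it is blank, the patient is taken to be out of hospital.

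Three other places bear on the point:

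- Protocol 6.6: every hospitalised state on the OSCI scores 3 or more.
- Protocol 8.5.1: relapse after recovery is a score above 1.
- SAP 7.3.1.1: missing post-baseline scores are filled from other data sources for death only.

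**The concern.** A missed OSCI day is not always an unknown day. If the CRF places the patient in hospital, the score could only have been 3 or more had it been taken, which is incompatible with sustained recovery. SAP 5.3.1.1 already draws this inference from the location field for discharge. SAP 5.3.1.2 instead counts the day as one of the 3 tolerated gaps.

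What is at stake is a wrong value on a primary endpoint in the presence of recorded data that contradict it. The recovery date is set too early or, if the patient does not stay at 1 or below after the window, a non-recovery becomes an event. The error carries into recovery by Days 7, 14, 21 and 28, because SAP 9.3.2.1 treats a patient as recovered at every visit after the first confirmed recovery. No planned analysis would show it: SAP 9.1.2.3 repeats the withdrawal-related missing-data methods and the subgroups for recovery, and the 7-day readmission analysis in SAP 9.1.1.3 is written for discharge.

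**Working it through.** The plan states no figure for this rule, so there is none to reproduce. The check applies the two rules literally and then bounds the number of patients.

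**Short stay.** OSCI is 1 on Days 10 and 11; the patient is in hospital on Days 12 to 14 with scores missed and location entered; OSCI is 1 from Day 15.

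| | Recovery (SAP 5.3.1.2) | Discharge (SAP 5.3.1.1) |
|---|---|---|
| Days 12 to 14 | 3 missing, allowed | location in hospital, status broken |
| Observed scores, Days 11 and 15 to 17 | all 1, condition met | all 2 or below |
| Result | recovered, dated Day 10 | Day 10 rejected; restarts at Day 15 |

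If the patient stays well, the recovery date is 15 − 10 = 5 days too early. If the patient scores 2 from Day 18, the literal rule still gives recovery on Day 10. Once the hospital days are used, neither Day 10 nor Day 15 qualifies.

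**All short patterns.** Take every 7-day window with 1, 2 or 3 missed days, all located in hospital, and a score of 1 on the other days. There are 7 + 21 + 35 = 63 patterns.

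- Literal recovery rule: 63 of 63 confirmed.
- Discharge rule: 0 of 63 pass.
- Recovery rule with missed in-hospital days treated as above 1: 0 of 63 confirmed.

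If the window is read as 6 further days there are 6 + 15 + 20 = 41 patterns, and the results are 41, 0 and 0.

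**Longer stay.** Scores are missed in hospital on Days 12 to 16, with OSCI 1 from Day 17. The windows starting from Days 10 and 11 each have 5 missing scores and are rejected. Day 17 is confirmed, which is correct without using location. If no later recovery is confirmed, the patient is censored at the assessment before Day 10, although the CRF shows non-recovery up to at least Day 16.

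**Size.** Inputs are from Protocol 8.1: 305 per arm, 30% placebo recovery at Day 28, hazard ratio 1.7, and 25% exponential dropout over 28 days. With recovery rate λ and dropout rate ω, the probability of an observed recovery is λ/(λ+ω) × [1 − exp(−28(λ+ω))].

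- 28ω = ln(100/75) = 0.288; placebo 28λ = ln(100/70) = 0.357; SNG001 28λ = 1.7 × 0.357 = 0.606.
- Placebo: 0.357/0.644 × (1 − e^−0.644) = 0.263, and 305 × 0.263 = 80.
- SNG001: 0.606/0.894 × (1 − e^−0.894) = 0.401, and 305 × 0.401 = 122.
- Total: about 202.

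The documents give no readmission rate. Assume that 3% to 5% are readmitted within 7 days of the first score of 1 or below, and that 20% to 50% of those have missed scores:

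- low: 202 × 0.03 × 0.2 = 1.2
- high: 202 × 0.05 × 0.5 = 5

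The simulation text in SAP Section 6 uses a recovery hazard ratio of 1.35. That gives about 183 events and a range of 1.1 to 4.6, which does not change the picture.

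**The case against.** The strongest reply is that the case is rare and often detects itself. After discharge, Protocol 6.6 scores the patient from two questions about the past 24 hours, one of which asks whether usual activities are back to the pre-infection level without extra help or oxygen. The short-stay example needs a yes on the day after leaving hospital. A no gives OSCI 2, an observed score that already breaks recovery. This stands. The 63 of 63 result shows what the rule permits, not how often it happens, and the range of 1 to 5 is nearer an upper bound because it ignores this and the other conditions (at most 3 missed scores, no withdrawal or death in the window).

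A second reply is that the endpoint requires no rebound at subsequent assessments, that a missed assessment is not an assessment, and that location cannot separate OSCI 1 from OSCI 2. This explains why location cannot confirm recovery. It does not explain why a recorded hospital day should not rule recovery out.

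Three stronger readings are tempting, and the documents do not support them:

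- A reader might infer that longer readmissions are generally censored early because of the relapse. SAP 5.3.1.2 first tests for a later recovery, so this applies only where none is confirmed.
- A reader might infer that recovery must always imply discharge under the SAP. Discharge must also hold up to Day 35 or withdrawal, whereas recovery needs only 7 days. With complete data, a patient recovered on Day 10 and readmitted on Day 20 already differs on the two endpoints.
- A reader might infer a bias towards SNG001. The trial is double-blind with one rule for both arms, and nothing shows in which arm such cases would fall.

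**Conclusion.** The point holds as a small correction. As written, SAP 5.3.1.2 can classify a patient as having sustained recovery while the CRF places that patient in hospital on up to 3 days of the rebound window, and no other rule in the SAP repairs this. The secondary consequence, censoring just before the possible recovery date despite known later hospital days, is limited to patients with more than 3 missed scores and no later confirmed recovery.

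The effect is a handful of patients at most, possibly none. The figure of 1 to 5 among about 202 expected recoveries rests on assumed readmission and missed-score rates that the documents do not give. No effect on the hazard ratio, power or direction of bias is shown. The case for acting is that the rule gives a wrong answer on a primary endpoint where the right one is already recorded.

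**What to change.** Add to SAP 5.3.1.2, in substance:

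*A missed OSCI assessment in the rebound period for which the CRF location is In Hospital is treated as OSCI above 1. It is a rebound and is not one of the 3 permitted missing scores. If no later recovery is confirmed, it is used as a known not-recovered date when the censoring date is set. Missed assessments with location Not in Hospital or unknown remain under the 3-missing allowance.*

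The cost is these few lines and a small change to the derivation program. The location field is already needed for SAP 5.3.1.1, so nothing new is collected. The change should be settled before unblinding; after that, SAP 7.4.5 requires it to be documented in the clinical study report as a change made after unblinding. It will not make the two primary endpoints fully consistent, because the different periods for which discharge and recovery must hold remain.

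### The SAP's time-to-recovery formula leaves out the 7-day sustained condition and contradicts the definition of recovery in the same section

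*SAP*

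**What the plan says.** SAP 5.3.1.2 sets the event: "Recovery will be defined as the first post baseline OSCi score of" 1 or below "which is sustained for 7 days". It allows up to 3 missing assessments in the 7-day period. With more than 3 missing, the patient does not count as recovered at that date and "sustained recovery will be reassessed at the subsequent OSCi assessment" of 1 or below. The window is also fixed: "Recovery will be derived for all scheduled post-baseline assessments up to Day 28".

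The section then turns to the event time: "Time to recovery (in days) for recovered patients will be calculated as the following". The line that follows begins "Date of first OSCi score of" 1 or below, from which the randomisation date is subtracted and 1 added. Neither a sustained nor a confirmed score is mentioned.

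The matching formula for the other primary endpoint, in SAP 5.3.1.1, begins "Date of first hospital discharge". There the date is that of the defined event, and the definition of that event already contains the sustained condition.

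**The concern.** Time to recovery is one of two primary endpoints and is tested under the Hochberg procedure (SAP 7.6). The formula is the line a programmer would code. The words limiting it to recovered patients settle who enters the formula, but not which of a patient's scores supplies the date. Two programmers, one working from the definition and one from the formula, could produce different event times for the same patient.

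Transient scores are plausible here. Under Protocol 6.6, after discharge the step between scores 1 and 2 depends on one daily yes/no answer about usual activities in the past 24 hours. The resulting score may not be adjusted when other assessments conflict with it. The 7-day rebound period is there to deal with such reversals.

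**Working it through.** The plan states no figure to reproduce, so the check compares the texts and then applies both dating rules to example patients.

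**Texts side by side**

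- *SAP 5.3.1.2, definition:* first score of 1 or below that is sustained for 7 days.
- *SAP 5.3.1.2, missing-data rule:* a score that cannot be confirmed because more than 3 assessments are missing is not the recovery date, and a later score may be.
- *SAP 5.3.1.2, latest date:* Day 28, because OSCI is collected to Day 35. This only makes sense if the recovery date opens a 7-day sustained period (28 + 7 = 35).
- *SAP 6:* the power simulation names its variable as time to sustained recovery.
- *SAP 9.1.2.1, Table 11:* the time to recovery is used where recovery lasted 7 days.
- *SAP 9.3.2.1:* by-visit recovery is counted from the first confirmed recovery.
- *SAP 15:* a fixed 7-day rebound period applies to both endpoints.
- *SAP 5.3.1.2, formula:* first score of 1 or below, with no further condition.

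Only the formula lacks the condition. Its clash with the missing-data rule is direct. If a patient's first score of 1 or below is rejected as unconfirmed and the patient recovers later, the formula returns the rejected date.

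**Both rules applied**

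Inputs, all assumed for illustration: randomisation on Day 1, so time = day of the chosen score − 1 + 1; score 4 on every day before the first score of 1. The defined rule requires all observed scores in the next 7 days to be 1 or below, with at most 3 missing.

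| Assumed scores | Defined rule | Formula as written | Days early |
|---|---|---|---|
| 1 from Day 6 on | 6 | 6 | 0 |
| 1 on Day 6, 2 on Day 7, 1 from Day 8 | 8 | 6 | 2 |
| 1 on Day 6, Days 7–10 missing, 1 from Day 11 | 11 | 6 | 5 |
| 1 on Days 6–7, 2 on Days 8–14, 1 from Day 15 | 15 | 6 | 9 |
| 1 on Day 2, 2 on Days 3–27, 1 from Day 28 | 28 | 2 | 26 |

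**Two consequences within the outputs**

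- In the fourth row, the SAP 9.3.2.1 rule counts the patient as not recovered at Days 7 and 14 and recovered at Days 21 and 28. The formula as written places recovery at Day 6, so the primary and secondary outputs would disagree about the same patient.
- Suppose that patient had been back in hospital with a score of 3 on Days 8 to 14. Sustained discharge under SAP 5.3.1.1 is then dated 15 days and literal recovery 6 days, so recovery would precede discharge.

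**What does not change**

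The definition decides who is an event. A patient whose only scores of 1 or below are transient is not recovered and is censored under SAP 5.3.1.2. Only the event times of patients who later have a sustained recovery can move, so the event count is the same under both rules.

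**The case against.** The best defence is that the formula is shorthand. It stands below a definition that fixes the sustained score, it is restricted to recovered patients, and every related section of the SAP points the same way. A careful programmer would read it in context. The discharge formula also depends on context, because the date of first discharge could be misread as a first physical discharge before a readmission.

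Most of this stands. The intent is clear, and the wrong date arises only if the line is coded against the definition above it. The defence does not remove the contradiction: the discharge line names a defined event, whereas the recovery line names a raw score and so states a different date.

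Three stronger readings are tempting, and the documents do not support them:

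- **That the sponsor plans to date recovery from unsustained scores.** No other part of the SAP says so, and several sections say the opposite.
- **That the reassessment sentence covers any score that fails to qualify.** It covers only the case of more than 3 missing assessments. A rebound to 2 is handled by the definition itself.
- **That a known share of recoveries is misdated.** With assumed daily fall-back rates of 3%, 6% and 10%, a simple daily simulation gives about 5%, 8% and 12% of recoveries dated wrongly, by about 9 days on average. A different simple model over the same 3% to 10% range gives 2% to 14% and 11 to 12 days. These figures come from the assumed inputs, because the documents give no fall-back rate.

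**Conclusion.** The formula is wrong as written. It omits a condition that the definition in its own section requires, and read literally it can return a date that the section rules out. In the example patients the error is 0 days without a transient or unconfirmed score, and 2 to 26 days with one. The main example gives 6 instead of 15 days. These sizes rest on assumed score sequences and randomisation on Day 1.

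The point is limited. The intended endpoint is clear, the number of events is unaffected, and only recovered patients with an earlier unsustained or unconfirmed score are touched. A reader might infer that the hazard ratio is biased in favour of SNG001 or that the type I error is inflated. The documents do not support either inference: the same rule applies in both blinded arms, and nothing is said about how often transient scores occur in either arm. The size and direction of any effect on the hazard ratio cannot be computed from what is given.

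**What to change.** In SAP 5.3.1.2, replace the formula with: date of the first OSCI score of 1 or below that meets the 7-day sustained-recovery definition, minus date of randomisation, plus 1. This matches the first confirmed recovery already used for the Day 7, 14, 21 and 28 analyses in SAP 9.3.2.1, so those need no new rule.

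Check the derivation program before unblinding. Test patients should include one with a rebound and one with more than 3 missing assessments after a first score of 1 or below. The event time should equal the date of first confirmed recovery in the by-visit analysis for every recovered patient.

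The cost is one line of text and a short programming check. No new data are needed, and the intended analysis stays the same. If the correction comes after unblinding, SAP 7.4.5 requires changes to the planned analysis to be documented in the clinical study report.
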